5.2. Exclusion Criteria

Individuals are not eligible for participation in this trial if any of the following criteria apply:

Medical History and Concurrent Conditions			
1.	Current or past history of significant cardiovascular, pulmonary, gastrointestinal, renal, hepatic, metabolic, genitourinary, endocrine (including diabetes mellitus), malignancy (except for basal cell carcinoma of the skin and cervical carcinoma in situ, at the discretion of the investigator), hematological, immunological, neurological, or psychiatric disease that, in the opinion of the investigator or medical monitor, could compromise either participant safety or the results of the trial.		

2.	"Yes" responses for any of the following items on the C-SSRS (within the individual's lifetime):	
	 Suicidal Ideation Item 3 (Active Suicidal Ideation with Any Methods [Not Plan] without Intent to Act) 	
	 Suicidal Ideation Item 4 (Active Suicidal Ideation with Some Intent to Act, without Specific Plan) 	
	Suicidal Ideation Item 5 (Active Suicidal Ideation with Specific Plan and Intent)	
	 Any of the Suicidal Behavior items (Actual Attempt, Interrupted Attempt, Aborted Attempt, Preparatory Acts or Behavior) 	
	"Yes" responses for any of the following items on the C-SSRS (within past 12 months):	
	Suicidal Ideation Item 1 (Wish to be Dead)	
	Suicidal Ideation Item 2 (Non-Specific Active Suicidal Thoughts)	
	Serious risk of suicide in the opinion of the investigator is also exclusionary.	
3.	History of substance or alcohol-use disorder (excluding nicotine or caffeine) as per DSM-5 criteria within 12 months prior to signing the ICF.	
4.	Any condition that could possibly affect drug absorption, including, but not limited to, complicated appendectomy or cholecystectomy, bowel resections, bariatric weight loss surgery, gastric banding, or gastrectomy.	
5.	Receipt of SARS-CoV2 vaccination or booster as follows:	
	mRNA: within 14 days prior to dosing	
	Non-mRNA: within 28 days prior to dosing	
	In addition, participants who plan to receive SARS-CoV2 vaccination or booster while participating in the trial or for at least 14 days after the last dose of IMP will be excluded.	
6.	Have recently been diagnosed with symptomatic COVID-19 or test positive for COVID-19 within 30 days prior to signing the ICF.	
Prior or Con	comitant Therapies	
7.	Use of prohibited medication prior to randomization or likely to require prohibited concomitant therapy (eg, prescription and over-the-counter medications, herbal medications, vitamins, and supplements) during the trial (see Section 6.5).	
Laboratory 7	Test Results	
8.	Either of the following: • History of HIV, hepatitis B, or hepatitis C infection	
	 Positive result for HIV, hepatitis B surface antigen, hepatitis B core antibody, or hepatitis C antibody 	
9.	Positive drug screen (including nicotine) or a positive test for alcohol (note: individuals who test positive for nicotine or alcohol may be rescreened).	
10.	Any of the following clinical laboratory test results (and confirmed by a single repeat measurement, if deemed necessary):	
	• AST or ALT ≥1.5 × ULN	
	 Total bilirubin ≥1.5 × ULN. Individuals with a history or suspicion of Gilbert's syndrome may be eligible provided the direct bilirubin is <uln.< li=""> </uln.<>	

11.	Estimated glomerular filtration rate at Screening <90 mL/min/1.73 m2, as calculated using the Chronic Kidney Disease Epidemiology Collaboration (CKD-EPI) equation (Levey et al, 2009).	
Other Exclusion	onary Assessments	
12.	12-lead ECG demonstrating any of the following at Screening or initial Check-in (Day -1): • QTcF interval >450 ms • QRS interval >120 ms • PR interval >220 ms Note: at Screening, eligibility will be determined based on the average of a centrally read triplicate set of ECGs. At initial Check-in (Day -1), a single ECG will be obtained. If any of the above criteria are not met at subsequent Check-ins, consult the medical monitor to determine whether the participant remains eligible to continue in the trial.	
13.	Blood pressure measurements demonstrating any of the following at Screening or Check-in (Day -1 of each period): • Systolic blood pressure ≥140 mmHg or diastolic blood pressure ≥90 mmHg • Blood pressure will be measured after at least 3 minutes in supine position. At Screening, the average of 2 measurements will be used to determine eligibility and a single measurement at each Check-in. • Orthostatic hypotension, defined as a decrease of ≥20 mmHg in systolic blood pressure upon standing compared with the supine blood pressure measurement (at Screening, relative to the average measurement) • Symptomatic orthostatic dizziness	
14.	Heart rate <45 bpm or >100 bpm based on vital signs assessment (rather than ECG). Heart rate will be measured in a supine position after at least 3 minutes of rest. The average of 2 measurements taken 1-2 minutes apart will be used to determine eligibility at Screening and a single measurement at each Check-in.	
15.	Any other abnormal safety findings unless, based on the investigator's judgment, the findings are not medically significant and would not impact the safety of the participant or the interpretation of the trial results. The medical monitor should be contacted to discuss individual cases, as needed. Tests with abnormal results may be repeated to ensure the reproducibility of the result before excluding a potential participant based on criteria provided in the protocol.	
Lifestyle or Ot	her Miscellaneous Exclusions	
16.	Refusal to abstain from grapefruit-containing foods or beverages or Seville orange-containing foods or beverages from 7 days prior to Day -1 through Check-out from the clinic for each treatment period.	
17.	Current use of tobacco or nicotine-containing products (cigarettes, cigars, chewing tobacco, snuff, e-cigarettes, etc).	
18.	History of chronic consumption of >400 mg/day of caffeine-containing drinks or food (eg, >4 cups [8 ounces] of brewed coffee, 9 cans [12 oz] of diet cola, 12 cans [12 oz] of cola, 8.5 cups of brewed black tea, 2 energy shot drinks).	
19.	Refusal to adhere to lifestyle considerations as defined in Section 5.3.	
20.	Considering or scheduled to undergo any surgical procedure during the trial.	
	Any other condition that would preclude IMP administration or trial participation (eg, difficulty swallowing, poor venous access).	

22.	Known allergy or hypersensitivity to the IMP, closely related compounds, or any of their specified ingredients.
23.	Donated more than 500 mL of blood in the 2 months prior to signing the ICF.
24.	Current enrollment or past participation within 30 days or 5 half-lives (whichever is longer) prior to signing the ICF in any other clinical trial involving an IMP.
25.	Employee of the investigator, clinic, or sponsor with direct involvement in the proposed trial or other trials under the direction of the investigator or clinic, as well as family members of the employee or investigator.
26.	Anyone who should not participate in the trial in the opinion of the sponsor, investigator, or medical monitor.
27.	Part B only: anyone who participated in Part A of the trial.

Abbreviations: ALT=alanine aminotransferase; AST=aspartate aminotransferase; COVID-19=coronavirus disease-2019; C-SSRS=Columbia-Suicide Severity Rating Scale; DSM-5=Diagnostic and Statistical Manual of Mental Disorders, 5th edition; ECG=electrocardiogram; ICF=informed consent form; IMP=investigational medicinal product; mRNA=messenger ribonucleic acid; QTcF=QT interval corrected for heart rate using Fridericia's formula; SARS-CoV2=severe acute respiratory syndrome coronavirus 2; ULN=upper limit of normal.

5.3. Lifestyle Considerations

5.3.1. Meals and Dietary Restrictions

Participants are required to abstain from consumption of caffeine-containing foods or caffeinated beverages (eg, coffee, tea, cola, energy drinks), grapefruit-containing foods or beverages, and Seville orange-containing foods or beverages from 7 days prior to Day -1 through Check-out from the clinic for each treatment period.

On days with intensive ECGs (extractions by central ECG service) and PK collection (Day 1 in Part A, Days 1 and 14 in Part B), participants will fast for at least 10 hours prior to dosing and remain fasting for the first 4 hours following dosing with a small snack given right after the 4-hour time point and lunch right after the 6-hour time point. Participants must abstain from all food and drink (except water) for at least 4 hours prior to any safety laboratory evaluations. Water is permitted until 1 hour prior to IMP administration and can be consumed ad libitum after dosing.

Meals consist of a light breakfast (~0700 hours, 1 hour prior to dosing), lunch (~1200 hours, 4 hours after dosing), and dinner (~1800 hours), and an evening snack (~2130 hours).

The following guidelines apply for dosing under "fed" conditions during food effect evaluation:

- Following an overnight fast of at least 10 hours, participants should start breakfast approximately 25 minutes prior to administration of IMP.
- The entire breakfast will be consumed approximately over a 20-minute period with the IMP administered within approximately 5 minutes of completion of the meal. Actual start and stop times for breakfast and IMP administration time will be recorded.

- There are no water restrictions prior to dosing for participants dosed under fed conditions. The IMP should be administered with 240 mL of ambient temperature water.
- No water is permitted for at least 2 hours postdose. No food will be allowed for at least 4 hours postdose.
- The breakfast will be a high calorie/high fat meal (approximately 150, 250, and 500-600 calories from protein, carbohydrate, and fat, respectively) consisting of 2 eggs fried in butter, 2 strips of bacon or 50 g of meat or sausage, 2 slices of toast with butter, 4 ounces of hash brown potatoes, and 8 ounces of whole milk.

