5.3.1 Meals and Dietary Restrictions	Added statement that no water is permitted for at least 2 hours postdose	To avoid potential abdominal distension

Section # and Name ^a	Description of Change	Brief Rationale
6.1 Trial Treatments Administered	CVL-354 Solution: Added unit dose strength	To align with current sponsor standards
	Added actual doses for Part A Cohorts 1 and 2 and starting dose for Part B Cohort 1	To reflect results obtained during Part A dose escalation
6.1 Trial Treatments Administered	CVL-354 Capsules: Completed corresponding rows of table, including anticipated dosage levels for Part A Cohort 3 and Part B Cohorts 2-5	To provide information on capsule IMP, including anticipated doses based on results obtained during Part A dose escalation
6.1 Trial Treatments Administered	Placebo: Provided corresponding information regarding capsule dosage form	To provide information on capsule IMP
6.1 Trial Treatments Administered	Overall: Revised presentation	To align with current sponsor standards
6.2 Preparation, Handling, Storage, and Accountability	Deleted mention of "suspension"	For consistency with revisions in Section 6.1 (Table 10)
6.3.1 Participant Assignment to Treatment	Added content on randomization to treatment sequence for food effect cohort	To provide relevant details
6.3.1 Participant Assignment to Treatment	For text about mirror randomization number, specified that Part A applies to Cohorts 1 and 2	To provide relevant details
6.3.2 Blinding	Added sentence that treatment assignment will not be blinded for food effect portion	To provide relevant details
6.3.2 Blinding	Removed text regarding documentation of unblinding in eCRF	To incorporate updated sponsor standard language
8.3.3 Vital Sign Measurements	Revised definition of orthostatic hypotension, including calculation relative to supine assessments	To correct errors from previous protocol version
10.2 Appendix 2: Clinical Laboratory Tests	Added a row for "Additional Required Tests" and added serum cystatin-C and urine β-2-microglobulin as additional safety laboratory tests to be taken	To permit appropriate evaluation of renal function following multiple doses
10.6 Appendix 6: Kidney Safety for First-in-Human Trial	Added a new appendix with guidance regarding the monitoring of kidney function	To provide additional safety monitoring in this first-in-human trial
11 References	Added supporting references	

Section # and Name ^a	Description of Change	Brief Rationale

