e Medical occurrences that begin before the start of IMP dosing but after obtaining informed consent will be recorded as medical and/or psychiatric history.

- f An alcohol test (breathalyzer or blood/urine) is required at Screening and at Check-in. The alcohol test may be conducted at any time during the trial at the discretion of the investigator.
- g Period 1 only.
- h Full physical and neurological examinations should be completed at Screening and Check-out (or ET). A limited examination (cardiovascular, pulmonary, and gastrointestinal) should be completed at Check-in. Symptom driven physical and/or neurological examinations may be done at any time point during the trial at the investigator's discretion.
- ¹ Triplicate ECGs will be obtained to confirm eligibility at Screening. Single ECGs will be obtained at all other time points.
- j Blood pressure and heart rate measurements will be obtained from participants in a supine position after at least 3 minutes of rest.
- k Orthostatic blood pressure and heart rate measurements will be obtained from participants in the standing position.
- ¹ The "Baseline/Screening" C-SSRS form will be completed for all participants at Screening to determine eligibility. The "Since Last Visit" C-SSRS form will be completed at Check-in to ensure that the participant continues to qualify for the trial and will also be completed at Check-out (or ET).
- m Concomitant medications should be recorded from Screening through the participant's last visit/contact.
- ⁿ Adverse events (serious and nonserious) will be recorded from first dose of IMP through the participant's last visit/contact.
- o Additional urine drug screening can be conducted at any time during the trial at the discretion of the investigator.
- ^p A confirmatory FSH is required for all post-menopausal women.
- ^q Predose PK samples (1 sample and 1 backup sample) will be obtained within 15 minutes prior to dosing.
- Future biospecimen research sample is optional and is only to be collected if signed consent is obtained from the participant. Sample can be collected at any time prior to initiation of first dose.
- ^s Dose to be administered after a high-fat breakfast during fed period and under fasted conditions during fasted period. Further details on fed and fasting conditions are provided in Section 5.3.1.

Confidential Page 30 of 96 Version 3.0: 25 May 2022

Table 3: Schedule of Assessments – Part B, Multiple Ascending Dose (Cohorts 1 to 5)

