4.1.1.2. Food Effect Evaluation (Cohort 3)

Cohort 3 will be scheduled after completion of single dose escalation to evaluate the effect of food on CVL-354 exposures after a single 50 mg dose. The selected dose is 4-fold lower than the top single CVL-354 200 mg dose that is considered to be safe and tolerated. For evaluation of food effect, a 2-period crossover design will be utilized, with approximately 8 participants randomized to 1 of 2 sequences (fed/fasted or fasted/fed). Details of fasted and fed conditions are provided in Section 5.3.1. Sentinel dosing will not be employed for evaluation of food effect.

Participants will remain domiciled after Check-in for both periods of the food effect evaluation. The duration of each period will be 3 days, with a 2-day washout between Period 1 and Period 2.

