9.4.3. Pharmacokinetic Analyses

All PK exposure parameters (eg, C_{max}, AUC) will be summarized by dose, where applicable, using descriptive statistics including the arithmetic mean, median, standard deviation, coefficient of variation, minimum and maximum values, Q1, Q3, and geometric mean.

For food effect assessment, the single dose of CVL-354 administered in fasted state is the reference treatment and the single dose of CVL-354 administered in fed state is the test treatment. Natural log-transformed dose-normalized AUC_{inf}, AUC_{last}, and C_{max} (for CVL-354) will be analyzed using a mixed effect model with sequence, period, and fast/fed status as fixed effects and participant within sequence as a random effect. Estimates of the adjusted mean differences (test-reference) and corresponding 90% CIs will be obtained from the model. Then they will be exponentiated to provide estimates of the ratio of adjusted geometric means (test/reference) and 90% CIs for the ratios.

Additional detail on the PK analysis will be provided in the SAP.

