### 6.4 Dose Administration

- All doses in Parts A, except for dosing under “fed” conditions, will be administered under fasted conditions following an overnight fast of at least 10 hours. Participants will continue to fast for 4 hours following dosing on Day 1.
- For dosing under “fed” conditions during food evaluation, following an overnight fast of at least 10 hours, participants will start breakfast approximately 25 minutes prior to administration of IMP. The IMP will then be administered within approximately 5 minutes of completion of the meal.
- For Part B, on days with intensive PK sampling (Day 1 and Day 14), the IMP will be administered under fasted conditions following an overnight fast of at least 10 hours. Participants will continue to fast for 4 hours following dosing on these intensive PK sampling days. On other days, each dose of IMP will be administered at approximately the same time each morning at least 1 hour following the morning meal.
- Each dose will be administered with 240 mL of water.

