### **SAD and Food effect**

Serial PK blood samples (1 sample and 1 backup sample) will be collected during the SAD portion for each participant receiving drug and placebo at predose, 0.5, 1, 2, 3, 4, 6, 8, 12, 16, 24, 36, and 48 hours postdose. Predose PK samples (1 sample and 1 backup sample) will be obtained within 15 minutes prior to dosing.

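### Cohort 3 bars water for 2 hours after the fed dose but not after the fasted dose, so any effect of early postdose water enters the fed/fasted ratio

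*Protocol*

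**What the plan says.** Protocol Section 5.3.1 has a list that applies only to fed dosing in the food-effect evaluation. One item reads "No water is permitted for at least 2 hours postdose". The Version 3.0 summary of changes gives the reason for adding it: "To avoid potential abdominal distension".

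For the fasted period the reader is sent to the same section. Section 4.1.1.2 says "Details of fasted and fed conditions are provided in Section 5.3.1", and footnote s of the Cohort 3 schedule (Table 2) says "Further details on fed and fasting conditions are provided in Section 5.3.1". Section 5.3.1 has no separate list for fasted dosing in Cohort 3. What it has is the general paragraph for intensive ECG and PK days, which names Day 1 in Part A and states: "Water is permitted until 1 hour prior to IMP administration and can be consumed ad libitum after dosing".

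PKAP 6.4 (SAP Appendix 9.5) gives the dosing water, "Each dose will be administered with 240 mL of water", and no postdose water rule for either period.

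Under Protocol 9.4.3, the exposure parameters are "analyzed using a mixed effect model with sequence, period, and fast/fed status as fixed effects", with participant within sequence as a random effect. PKAP 9.2 uses the same terms.

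**The concern.** The crossover is meant to isolate the effect of the meal. Other postdose conditions are held alike: the same dosing water and a 4-hour postdose fast in both periods. Postdose water is the exception, and it is not part of the intended contrast.

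The stated reason explains why water is withheld after a large meal. It does not explain why the reference period was left unrestricted. If early water changes how the 50 mg capsule dose is absorbed, the change appears as food effect, and the confidence interval gives no sign of it.

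Food effect is a listed secondary objective, and Protocol 4.2 says that an effect seen at 50 mg may be carried over to lower doses.

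**Working it through.** The plan states no figure on this point. The check has three parts: the text, the model, and an illustration of size.

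**1. The rules side by side**

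| Condition | Fed period | Fasted period | Source |
|---|---|---|---|
| Water with dose | 240 mL | 240 mL | Protocol 5.3.1 (fed list); PKAP 6.4 |
| Food after dose | none for at least 4 h | none for 4 h | Protocol 5.3.1 |
| Water after dose | none for at least 2 h | no limit | Protocol 5.3.1 |
| Water before dose | no limit | none in the last hour | Protocol 5.3.1 |

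One reading problem needs settling. The general paragraph opens with days of intensive ECG extraction, and Table 2 has no Holter row for Cohort 3. However, the paragraph names Day 1 in Part A, and Cohort 3 is in Part A. If the paragraph did not apply, the fasted period would have no postdose water rule at all. Water is unrestricted after the fasted dose on either reading.

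**2. Can the model separate water from food?**

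Take 8 participants, 4 per sequence, 2 periods, with columns for intercept, sequence, period and fed status. This matrix has rank 4. Add a fifth column for the water rule: it equals the fed column in every participant-period, and the rank stays 4. The two effects cannot be separated. With a true food ratio of 1 and assumed rule effects of 0.90, 0.95, 1.05 and 1.10, the fitted fed/fasted ratio is 0.90, 0.95, 1.05 and 1.10. The rule effect passes through in full.

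Section 5.3.1 asks for breakfast and dosing times to be recorded but not water intake, so it provides no covariate for a later adjustment.

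**3. How large could it be?**

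The PKAP sampling times are "predose, 0.5, 1, 2, 3, 4, 6, 8, 12, 16, 24, 36, and 48 hours postdose". Of the 12 postdose samples, 3 (0.5, 1 and 2 h) fall within the 2-hour window.

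The documents give no water effect, no share of drinkers and no within-subject CV. The following inputs are assumptions:

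- share p of fasted participants who drink early: 0, 0.5 or 1
- change in Cmax among those who drink: 5% or 10%, direction unknown
- within-subject CV: 15%, 25% or 35%

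Shift in the log ratio = p × ln(effect):

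- p = 0: 0, factor 1.00
- p = 0.5: 0.5 × ln(1.05) = 0.0244, factor 1.025; 0.5 × ln(1.10) = 0.0477, factor 1.049
- p = 1: factor 1.05 or 1.10

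Precision, with 4 + 4 completers and 6 degrees of freedom:

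- log half-width of the 90% CI = t(0.95, 6) × 0.5 × σw = 1.943 × 0.5 × σw = 0.972 σw
- σw = √ln(1 + CV²)

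| CV | σw | Log half-width | 90% CI | Shift at p = 0.5 as share of half-width |
|---|---|---|---|---|
| 15% | 0.149 | 0.145 | ×/÷ 1.16 | 0.0244/0.145 to 0.0477/0.145 = 17% to 33% |
| 25% | 0.246 | 0.239 | ×/÷ 1.27 | 0.0244/0.239 to 0.0477/0.239 = 10% to 20% |
| 35% | 0.340 | 0.330 | ×/÷ 1.39 | 0.0244/0.330 to 0.0477/0.330 = 7% to 14% |

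**The case against.** The case for leaving the plan alone has four parts.

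- **No harm is shown.** Nothing in the documents says that early water alters CVL-354 absorption, and every input to the illustration is assumed. With 8 participants, the p = 0.5 shift lies well within the interval. Cmax may not fall inside the 2-hour window, and AUC sampled to 48 hours may be less sensitive. This stands as a limit on size. It does not remove the asymmetry: the shift would be systematic, and the interval does not reflect it.
- **No decision turns on the ratio.** There is no hypothesis test and no food-effect threshold. This also stands, and it is why the point is minor. The ratio is still the planned result of Cohort 3.
- **The fix is partial.** Predose water also differs between periods, and every component of the fed regimen is confounded with fed status. That is true, but the predose difference largely comes with a meal that starts about 25 minutes before dosing and includes 8 ounces of milk. The postdose difference does not come with the meal and can be removed.
- **Free postdose water is the trial's standard on fasted PK days.** Changing it only for Cohort 3 would make its fasted period differ from the other fasted profiles, including the 50 mg capsule cohort of Part B on Day 1. This is a real but secondary cost, because the planned comparison is within participants, fed against fasted.

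**Conclusion.** The concern holds. The postdose water rule differs between the two Cohort 3 periods on either reading of Section 5.3.1, and it cannot be separated from fed status in either model. What differs is permission to drink, not a fixed intake, so the effect may be nil; its direction is also unknown. Under the assumed inputs with half of fasted participants drinking early, the ratio moves by a factor of 1.02 to 1.05, or 7% to 33% of the log half-width of the 90% CI. The consequence is confined to the food-effect ratio. It is an avoidable confounder that is cheap to remove, not a threat to the trial's main conclusions.

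**What to change.** Add one sentence to Protocol Section 5.3.1 and repeat it in PKAP 6.4: in both periods of Cohort 3, no water is allowed for 2 hours after dosing, apart from the 240 mL given with the dose. This keeps the protection against abdominal distension in the fed period and makes the two periods alike after dosing. Predose water need not be matched, because the meal itself brings fluid.

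The cost is two sentences and 2 hours without water for fasted participants, plus the small loss of comparability with other fasted cohorts noted above. No procedures, participants or model terms are added.

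If Cohort 3 has already been dosed, report the different water rules as a limitation of the food-effect ratio.
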